## **7.2 PERFORMANCE**

The Investigator must demonstrate reasonable efforts to obtain qualified patients for the study. The Sponsor may terminate the study with any Investigator for any reason, including, but not limited to, Investigator nonperformance or Investigator noncompliance.

## **7.3 ACCOUNTABILITY**

Ironwood requires accountability of all study drug received and administered by the Study Center. Required records of drug disposition are to include logs or dispensing-records capturing, but not limited to, the date study drug was received, date(s) individual dosing units were prepared and labeled, date administered, quantity administered, and the subject to whom study drug was administered. At the end of the study, a complete reconciliation of the study drug supplies will be performed. All unused and reconciled drug supplies will be destroyed according to standard institutional policy or per written instruction from Ironwood should an alternate disposition be requested. No study drug is to be destroyed without prior written permission of Ironwood. A copy of the Certificate of Destruction or equivalent shall be provided to Ironwood once available.

## **7.4 RETENTION AND REVIEW OF RECORDS**

Records and documents pertaining to the conduct of this study, including eCRFs, source documents, ICFs, laboratory test results, and medication inventory records, must be retained by the Investigator in accordance with locally applicable regulatory requirements; and, in any event, for a minimum period of 5 years.

No study records shall be destroyed without notifying Sponsor and giving Sponsor the opportunity to take such study records or authorizing in writing the destruction of records after the required retention period.

If the Investigator retires, relocates, or otherwise withdraws from the responsibility of keeping the study records, custody must be transferred to another person (Ironwood, IRB, or other Investigator) who will accept the responsibility. Ironwood must be notified of and agree to the change.

## **7.5 PATIENT CONFIDENTIALITY**

All data collected in the context of this study will be stored and evaluated in such a way as to guarantee patient confidentiality in accordance with the legal stipulations applying to confidentiality of data. All patient records will be identified only by initials and patient identification (PID) number. Patient names are not to be transmitted to Ironwood or its authorized designee. The Investigator will keep a Master Patient List on which the PID number and the full name, address, and telephone number of each patient is listed.

| mmHg | millimeters of mercury |
| MPV | mean platelet volume |
| PCS | potentially clinically significant |
| PD | pharmacodynamic(s) |
| PK | pharmacokinetic(s) |
| PT | preferred term |
| RBC | red blood cell |
| RDW | red blood cell distribution width |
| RHI | reactive hyperemia index |
| SAE | serious adverse event |
| SAP | statistical analysis plan |
| SAS® | Statistical Analysis System |
| SOC | system organ class |
| $t_{1/2}$ | apparent terminal phase half-life |
| tau | dosing interval |
| TEAE | treatment emergent adverse event |
| T_{max} | sampling time of maximum observed plasma concentration |
| WBC | white blood cell |

1. INTRODUCTION

Study C1973-201 is a Phase 2a, open-label, single-center study in patients with Type 2 diabetes, hypertension and impaired endothelial function to evaluate the effect of escalating doses of IW-1973 on tolerability, endothelial function, and hemodynamics.

This statistical analysis plan (SAP) provides a more technical and detailed description of the data presentations and statistical analyses of the data as outlined and/or specified in the final protocol for Study C1973-201 (C1973-201-P-03, dated 09 January 2017). Specifications of tables, figures, and data listings are contained in a separate document.

2. STUDY OBJECTIVES

The objectives of the study are to evaluate the following in adult patients with stable type 2 diabetes mellitus and controlled hypertension:

- Safety and tolerability of escalating doses of IW-1973.
- Impact of escalating doses of IW-1973 on
 - endothelial function using EndoPAT™ to measure fingertip small vessel pulse volume
 - blood pressure (BP) and heart rate

3. STUDY DESIGN

3.1 GENERAL DESCRIPTION

This open-label, single-center trial will enroll 12 patients (at least 4 men and 4 women) to receive once-daily study drug for 6, sequential, 3-day dosing cycles (18 total days) starting with placebo (baseline) for 3 days and then progressing to 5 escalating dose levels of IW-1973 (10, 20, 30, 40, and 50 mg) for 3 days each. Patients will be in clinic for 20 days, from Check-in on Day -1 to Discharge on Day 19. Total patient participation will be 45 to 77 days.

3.2 DISCUSSION OF STUDY DESIGN, INCLUDING THE CHOICE OF CONTROL GROUPS

In this open-label study, patients will undergo 3 days of placebo dosing before beginning dosing with IW-1973, thereby serving as their own control. This design is sufficient for the stated objectives of this study.

3.3 TREATMENTS ADMINISTERED

Patients will receive once-daily (QD) study drug in the morning (8 to 10 AM) for 6 sequential, 3-day dosing cycles starting with placebo (2 tablets) for 3 days and then progressing to 5 escalating dose levels of IW-1973 (10, 20, 30, 40, and 50 mg) administered as multiple 5 mg tablets for 3 days each.

Nitroglycerin, 0.4 mg, sublingual tablet, will be administered to all patients at the Follow-up Visit to test endothelium-independent vasodilation.

3.4 METHODS OF ASSIGNING PATIENTS TO TREATMENT GROUPS

All patients will receive placebo and 5 escalating dose levels of IW-1973.

3.5 BLINDING

This is an open-label study.

4. DETERMINATION OF SAMPLE SIZE

The sample size in this trial was determined outside of statistical considerations. A sample size of 12 patients is considered sufficient and is based on precedent set by prior studies of similar nature.

**5. PHARMACOKINETIC, PHARMACODYNAMIC, AND
SAFETY ASSESSMENTS**

5.1 STUDY SCHEMATIC AND SCHEDULE OF ASSESSMENTS

The schedule of evaluations for Study C1973-201 is presented in the following table.

Table 1 Schedule of Events

| Visit Days → Study Procedure ↓ | Screening Period | Clinic Period | | | | | | Follow-up Period | |
|---|---------------------|--|---|---|--|---|--|---|---|
| | | Screening Visit (Day -28 to -2) | Check- in Day -1 | 1 st day of cycle Days 1, 4, 7, 10, 13, 16 | 2 nd day of cycle Days 2, 5, 8, 11, 14, 17 | 3 rd day of cycle Days 3, 6, 9, 12, 15, 18 | Discharge Day 19 | Follow-up Visit Day 32 (± 2 days) | End of Trial Visit Day 46 (± 3 days) |
| Informed consent signed | X | | | | | | | | |
| Inclusion/exclusion evaluation | X | X | | | | | | | |
| Demographics | X | | | | | | | | |
| Medical history | X | | | | | | | | |
| Physical exam | X | X | | | | | X | | X |
| HBsAg, HCV & HIV screen | X | | | | | | | | |
| Drug & alcohol screen (a) | X | X | | | | | | X | |
| Pregnancy test (b) | X | X | | | | | | X | X |
| Weight (W) & height (H) (c) | W, H | W | W | | | | W | W | W |
| 12-lead ECG (d) | X | X | pre: 0 (\leq 15m) pd: 1, 4h (\pm 15m) | | | | X | | |
| Respiratory rate & oral temp (e) | X | X | | | | | X | preNG: 0 (\leq 15m) | X |
| Clinical chemistry, coagulation, hematology, urinalysis (f) | X | X | | | | | X | preEndoPAT (\geq 1h) | |
| Hemoglobin A1c | X | X | | | | | X | preEndoPAT (\geq 1h) | |
| Fasting blood glucose & serum insulin (g) | X | X | | pre: 0 (\leq 15m) | | | X | preEndoPAT (\geq 1h) | |
| Adverse event evaluations | X | X | X | X | X | X | X | X | X |
| Prior & concomitant meds | X | X | X | X | X | X | X | X | X |
| EndoPAT (h) | X | X | | | pre: 0 (\leq 1h) pd: 4, 12h (\pm 15m) | | | preNG: 0 (\leq 1h) pdNG: 45m (\pm 15m) | |
| Supine/standing BP & pulse supine only (i) | X | ☒ | pre: 0 (\leq 30m) pd: 1, 2, 4, 8, 12h (\pm 10m) | | Supine only pre: 0 (\leq 30m) pd: 1, 2, 8h (\pm 10m) | 24h (\pm 15m) | Supine only preNG: 0 (\leq 30m) pdNG: 2h (+30m) | ☒ | |

| Visit Days → Study Procedure ↓ | Screening Period | Clinic Period | | | | | Follow-up Period | |
|-----------------------------------|--|------------------------|---|---|---|---------------------|---|---|
| | Screening Visit (Day -28 to -2) | Check- in Day -1 | 1st day of cycle Days 1, 4, 7, 10, 13, 16 | 2nd day of cycle Days 2, 5, 8, 11, 14, 17 | 3rd day of cycle Days 3, 6, 9, 12, 15, 18 | Discharge Day 19 | Follow-up Visit Day 32 (± 2 days) | End of Trial Visit Day 46 (± 3 days) |
| | | | | | | | | |
| Platelet function (k) | | | pre: 0 (\leq 15m) pd: 4h (\pm 15m) | | | | | |
| Pharmacokinetic samples (l) | | | pre: 0 (\leq 15m) pd: 1,3,6,12h (\pm 5m) | pre: 0 (\leq 15m) | | 24h (\pm 15m) | preEndoPAT (\geq 1h) | X |
| | | | | | | | | |
| | | | | | | | | |
| Study drug administration (o) | | | X | X | X | | | |
| Ambulatory BP monitoring | | | | Start: pre 0(\leq 30m) End: pd12h(+30m) | | | | |
| Confined to clinic | | X | X | X | X | | | |
| Discharge from clinic | | | | | | X | | |
| Nitroglycerin administration (p) | | | | | | | X | |
| Study completion | | | | | | | | X |

BP = blood pressure; ECG = electrocardiogram; EDTA = ethylenediaminetetraacetic acid; h = hour; H = height; HBsAg = hepatitis B surface antigen; HCV = hepatitis C virus; HIV = human immunodeficiency virus; ICF = informed consent form; m = minute; NG = nitroglycerin; pd = postdose; PD = pharmacodynamic; pre = predose; W = weight

- Urine drug screen for selected drugs of abuse and alcohol breathalyzer screen
- For female patients, a negative serum pregnancy test must be documented at the Screening Visit, at Check-in with results available before dosing, and at the End of Trial Visit; a negative urine pregnancy test must be documented at the Follow-up Visit before nitroglycerin dosing.
- On in-clinic days, in the morning after voiding, before any water or food intake
- Patients must be supine for \geq 5 m before the ECG recording (Note: if on initial ECG, QTcF is \geq 450 msec for men or is \geq 470 msec for women, the ECG will be repeated 2 more times, and the average of the 3 QTcF values will be used to determine the patient's eligibility); before blood draws where applicable
- Respiratory rate after the patient has been seated for \geq 5 m
- After \geq 8-h fast, after EndoPAT and BP/pulse measurements and before dosing, except at Follow-up Visit; left arm preferred. Urinalysis may be performed prior to EndoPAT and blood pressure assessments.
- Must fast \geq 8 hours; left arm preferred

5.2 PHARMACODYNAMIC ASSESSMENTS

The following hemodynamic, endothelial function and platelet function assessments will be performed throughout the study, as outlined in the Schedule of Assessments.

Ambulatory BP Monitoring:

Patients will undergo 12-hour ambulatory BP monitoring on the second day of each cycle, starting at predose (\leq 30 minutes) and ending at 12 hours postdose. 30-minute, 4-hour, and daytime averages of mean arterial pressure (MAP), systolic and diastolic BP, and pulse measurements will be calculated.

Supine and Orthostatic Pulse and BP Assessments:

Supine and standing BP and pulse measurements will be obtained on the first day of each cycle at 0, 1, 2, 4, 8, and 12 hours postdose. Supine measurements will also be obtained on the third day of each cycle at 0, 1, 2, 8, and 24 hours postdose, and at the follow-up visit prior to and 2 hours after the nitroglycerine dose.

For an individual patient, the supine BP and pulse determination at a particular timepoint will be based on a single measurement after the patient has been lying quietly for at least 5 minutes, and the standing assessment will be obtained 2 minutes after the patient has assumed the standing position after assuming sitting position for 1 minute after the supine assessment. The left arm will be used for BP measurements.

Orthostatic assessments, defined as the change in systolic and diastolic BP and pulse measurements after the patient has gone from the supine to the standing position, will be calculated.

Endothelial Function Assessments

Endothelial function in the finger will be measured using the noninvasive EndoPAT™ (Itamar Medical; Caesarea, Israel) device on the third day of each cycle at 0, 4, and 12 hours postdose, and at the follow-up visit prior to and 45 minutes after the nitroglycerine dose. All measurements will be performed in a quiet, dimly lit, temperature controlled room after the patient has been

resting quietly for 15 minutes. The right arm will be used for occlusion and finger measurements. Endothelial function will be assessed using the Reactive Hyperemia Index (RHI) parameter.

Platelet Function Assessments:

Blood samples for platelet function assessment using the PFA-100® instrument will be collected on the first day of each cycle. Platelet function will be assessed using time to adhesion /aggregation.

[REDACTED]

[REDACTED]

[REDACTED]

[REDACTED]

[REDACTED]

5.3 PHARMACOKINETIC ASSESSMENTS

Blood samples for PK assessments will be collected as outlined in the Schedule of Events. If systemic levels of IW-1973 are detectable, and data support the calculations, the following PK parameters may be calculated:

- AUC_{tau} : Area under the plasma concentration time curve during a dosing interval (tau);
- C_{max} : Maximum observed plasma concentration, occurring at T_{max} ;
- C_{trough} : Trough plasma concentration observed at the end of a dosing interval (collected before the next administration)
- $t_{1/2}$: Apparent terminal phase half-life (whenever possible);
- T_{max} : Time of maximum observed plasma concentration;

5.4 SAFETY ASSESSMENTS

The following safety assessments are performed throughout the study, as indicated in the Schedule of Events.

- Adverse Events
- Physical Examination
- Height and Weight
- Vital Signs including oral temperature, respiratory rate, pulse, and cuff BP measurements
- Laboratory Parameters
 - Serum Chemistry: albumin, alkaline phosphatase, alanine aminotransferase (ALT), aspartate aminotransferase (AST), bicarbonate, blood urea nitrogen (BUN), calcium, chloride, cholesterol, creatinine, gamma glutamyl transferase (GGT), glucose, HDL-c, lactate dehydrogenase (LDH), LDL-c (calculated), magnesium, phosphorus, potassium, sodium, total bilirubin, total protein, triglycerides, uric acid.
 - Hematology: hematocrit, hemoglobin, platelet count, mean platelet volume (MPV), RBC count, WBC count, WBC differential (basophils, eosinophils, lymphocytes, monocytes, and neutrophils [% and absolute]), RBC indices (mean corpuscular hemoglobin [MCH], mean corpuscular hemoglobin concentration [MCHC], and mean corpuscular volume [MCV]), red blood cell distribution width [RDW]).
 - Coagulation: activated partial thromboplastin time (aPTT), Prothrombin time, INR.
 - Urinalysis: pH and specific gravity, bilirubin, glucose, ketones, leukocytes, nitrates, occult blood, protein, urobilinogen, microscopic, including bacteria, RBCs, WBCs per high power field (HPF) only if dipstick is abnormal.
 - Additional tests: Hemoglobin A1c, fasting blood glucose, serum insulin
- 12-lead Electrocardiogram

6. STATISTICAL METHODS

6.1 GENERAL METHODOLOGY

Descriptive statistics (number of patients, mean, standard deviation, median, minimum and maximum) will be calculated for continuous variables. For summaries of continuous PK parameters, the geometric mean and the coefficient of variation (CV) will also be presented. For summaries of continuous PD parameters, the CV, 95% confidence intervals (CI), as well as the 25th and 75th percentiles will be presented. For categorical variables, frequencies and percentages for each category will be presented. Percentages will be based on the total number of patients with non-missing values. If there are missing values, the number missing will be presented, but without a percentage.

Inferential statistics, if calculated, will only be used for descriptive purposes.

All statistical analyses will be performed using SAS Version 9.1 or later [1]. Additional analyses using alternative software may be performed as part of the pharmacokinetic analysis.

Summary data will be presented by cycle group:

- Placebo
- IW-1973 10 mg
- IW-1973 20 mg
- IW-1973 30 mg
- IW-1973 40 mg
- IW-1973 50 mg

Definition of Baseline:

The following definitions of baseline will be used to calculate change from baseline parameters, unless specified otherwise-

- Study baseline is defined as the last non-missing assessment before first administration of study drug, that is, the Day -1 assessment.

- Time-matched baseline for each day/timepoint in the IW-1973 cycles is defined as the corresponding assessment during the placebo cycle.
- Cycle baseline is defined as the assessment taken prior to drug administration at the beginning of each cycle.
- Trough baseline is defined as the last assessment prior to initiation of IW-1973 administration, that is, the Study Day 4 predose assessment.

6.2 ADJUSTMENTS FOR COVARIATES

There are no adjustments for covariates planned for this study.

6.3 HANDLING OF DROPOUTS OR MISSING DATA

Missing observations will be treated as missing at random, and no imputation will be performed. All safety and tolerability data will be summarized and analyzed when data values are available for a patient. With respect to PK data, parameters will be derived as defined in Section 5.3 and although these methods may employ some inherent estimation of missing values (i.e., calculation of AUC), no formal imputation methods will be performed for the study.

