### **3.7.3.2 Vital Signs**

Vital signs will be measured according to the Schedule of Events and documented on the eCRF. Vital sign measurements include oral temperature (°C), respiratory rate, and supine and standing BP and pulse. Respiratory rate will be taken after the patient has been seated for at least 5 minutes. At the Screening Visit and at Check-in, the blood pressure assessments should be completed at medication trough level, i.e. prior to subjects taking their hypertensive medications. In addition, at the Screening Visit and at Check-in the supine BP measurements will be the average of 3 measurements obtained at 2-minute intervals after the patient has been lying quietly for at least 5 minutes; for supine only BP and pulse measurements thereafter, patient must lie quietly for at least 5 minutes before measurements are taken. For supine and standing BP and pulse measurements, patient must lie quietly for at least 5 minutes before supine measurements are taken, then assume a sitting position for 1 minute, and finally assume a standing position for 2 minutes before standing measurements are taken. All BP and pulse measurements should be taken in the arm not used for EndoPAT occlusion and before blood draws where applicable.

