## **5.3 ELECTRONIC CASE REPORT FORMS AND DATA MANAGEMENT**

All data relating to the study will be recorded in the patient's source documentation and eCRF to be provided by Ironwood or designee via the electronic data capture (EDC) system. Source documentation supporting the eCRF data should indicate the patient's participation in the study and should document the dates and details of study procedures, AEs, all observations, and patient status. The Investigator is responsible for verifying that all data entries on the eCRFs are accurate and correct and ensuring that all data are entered in a timely manner, as soon as possible after the information is collected. An explanation should be provided for any missing data. The Investigator must provide through the EDC system his or her formal approval of all the information in the eCRFs and changes to the eCRFs to endorse the final submitted data for each patient.

Ironwood will retain the final eCRF data and corresponding audit trails. A copy of the final archival eCRF in the form of a compact disc or other electronic media will be placed in the Investigator's study file.

A record of screen failures and pretreatment failures will be maintained for patients who do not qualify for enrollment, including the reason for the failure.

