7.9.3 Vital Signs Parameters

Vital signs evaluations at each assessment timepoint not included in the PD analyses and the corresponding change from study baseline will be summarized for each cycle group.

The number and percentage of patients who had a notable change from baseline in BP and pulse (based on the criteria in Table 3), will be presented by cycle group.

Table 3. Criteria for Notable Changes in Post-Baseline Vital Signs

| Vital Sign Parameter | Flag | Criteria* | |
|---|-------------|-----------------------|-----------------------------------|
| | | Observed Value | Change from Study Baseline |
| Supine/Standing Systolic Blood Pressure (mmHg) | High | ≥ 180 | Increase of ≥ 30 |
| | Low | ≤ 90 | Decrease of ≥ 30 |
| Supine/Standing Diastolic Blood Pressure (mmHg) | High | ≥ 105 | Increase of ≥ 20 |
| | Low | ≤ 50 | Decrease of ≥ 20 |
| Supine Pulse Rate (bpm) | High | ≥ 110 | Increase of ≥ 20 |
| | Low | ≤ 50 | Decrease of ≥ 20 |
| Standing Pulse Rate (bpm) | High | ≥ 120 | Increase of ≥ 30 |
| | Low | ≤ 50 | Decrease of ≥ 20 |

*A postbaseline value is considered as a notable value if it meets both criteria for observed value and change from baseline.

The number and percentage of patients who meet the following criteria at any postdose timepoint will also be summarized by cycle group:

- Orthostatic decrease in systolic BP of > 20 mmHg from supine to standing
- Orthostatic decrease in diastolic BP of > 10 mmHg from supine to standing
- Orthostatic increase in pulse of > 20 beats per minute from supine to standing

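### Standing readings lost because the patient was too symptomatic to stay upright are handled as missing at random, which can understate the orthostatic and standing-BP counts by cycle

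*SAP*

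**What the plan says.** **Procedure.** Protocol 3.7.3.2 has the patient lie for at least 5 minutes, sit for 1 minute and "finally assume a standing position for 2 minutes before standing measurements are taken". SAP 5.2 schedules standing readings on the first day of each cycle: one predose and five postdose (1, 2, 4, 8 and 12 h). Neither document says what is recorded if the patient cannot complete the stand.

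**Missing data.** SAP 6.3: "Missing observations will be treated as missing at random, and no imputation will be performed". It adds: "All safety and tolerability data will be summarized and analyzed when data values are available for a patient".

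**Denominator.** SAP 6.1: "Percentages will be based on the total number of patients with non-missing values", and "If there are missing values, the number missing will be presented, but without a percentage".

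**Counts.** SAP 7.9.3: "The number and percentage of patients who meet the following criteria at any postdose timepoint will also be summarized by cycle group". There are three criteria, for systolic BP, diastolic BP and pulse. The first is "Orthostatic decrease in systolic BP of > 20 mmHg from supine to standing". All three need a standing value. So do the standing flags in SAP Table 3, which require both an observed-value limit and a change limit to be met. SAP 7.7.2 also summarises the mean supine-to-standing change by cycle and timepoint.

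**Reason for missingness.** Protocol 5.3: "An explanation should be provided for any missing data". The SAP makes no use of that explanation.

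**The concern.** The drug lowers blood pressure: Protocol 1.2.1 reports dose-dependent falls in animals. All patients also take an ACE inhibitor or ARB, and Protocol 3.5.2 says the top dose exceeds the maximum tolerated level in healthy volunteers. A patient who has to sit down before the 2-minute standing reading is likely to be one whose pressure fell furthest. The reason the value is absent is then the value itself.

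The effect goes one way. A lost qualifying reading can remove a patient from a numerator for falls or low standing pressure, and cannot add one. If such losses become more frequent as the dose rises, which is plausible but not shown in the documents, the cycle-by-cycle comparison flattens where tolerability matters most. Safety and tolerability of escalating doses is the first listed objective, and Protocol 3.5.2 names as a secondary aim whether gradual escalation improves tolerability.

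**Working it through.** The plan gives no figure to reproduce. N = 12 was set outside statistical considerations, and no event rate, SD or missingness rate is stated. The check is a count under the SAP's own rules, followed by an illustration under stated assumptions.

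**1. What happens to a patient with one aborted stand in a cycle**

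| Other postdose standing readings that cycle | Treatment under SAP 6.1, 6.3 and 7.9.3 |
|---|---|
| At least one qualifies | Counted as an event |
| Some exist, none qualifies | Counted as a non-event, denominator unchanged |
| None exists | Leaves the denominator, appears in the number missing |

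**2. Effect on a cycle percentage.** Inputs: 12 patients dosed in the cycle; k true reactors (assumed, 1 to 4); one reactor missed entirely. True share = k/12. SAP share = (k − 1)/12 if other readings exist, or (k − 1)/11 if none does.

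| k | True | Other readings, none qualifying | No standing reading |
|---|---|---|---|
| 1 | 8.3% | 0/12 = 0% | 0/11 = 0% |
| 2 | 16.7% | 1/12 = 8.3% | 1/11 = 9.1% |
| 3 | 25.0% | 2/12 = 16.7% | 2/11 = 18.2% |
| 4 | 33.3% | 3/12 = 25.0% | 3/11 = 27.3% |

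One missed patient costs 8.3 points in the first case and 6.1 to 8.3 in the second. If two of three reactors are missed, 25.0% becomes 1/12 = 8.3% or 1/10 = 10.0%.

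**3. Chance that the reaction is missed entirely.** If each of the other four readings qualifies independently with probability q, the chance that none does is (1 − q)^4: 100% at q = 0, 32% at q = 0.25, 6% at q = 0.50.

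**4. Illustration (none of these inputs is in the documents).** Orthostatic systolic change has mean −8 or −12 mm Hg at all five timepoints, with between- and within-patient SDs of 8 mm Hg. A stand whose fall would exceed a cut is aborted, with probability 1 or 0.5, and is recorded as missing. The outcome is the share of patients with a fall above 20 mm Hg at one or more timepoints. Simulated true shares are about 38.5% (mean −8) and 55.0% (mean −12).

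| Mean | Cut | Understatement, all aborted | Half aborted | Still flagged, all aborted* |
|---|---|---|---|---|
| −8 | 25 | 9.5 points | 3.7 | 55% |
| −8 | 30 | 2.0 | 0.9 | 79% |
| −8 | 35 | 0.4 | 0.2 | 90% |
| −12 | 25 | 14.1 | 4.8 | 59% |
| −12 | 30 | 3.0 | 1.2 | 84% |
| −12 | 35 | 0.5 | 0.2 | 93% |

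*Share of patients with an aborted stand who still have another qualifying reading.

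Ten of these twelve settings lie below 5 points. With every such stand aborted, the mean fall is understated by about 0.3 mm Hg (mean −8, cut 35) to 2.7 mm Hg (mean −12, cut 25). The model holds the mean constant over the day. If the fall is concentrated near peak effect, fewer other readings qualify and more patients are missed, as step 3 shows for small q.

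**5. Mean at a single timepoint.** Assume eleven patients at −5 mm Hg and one at −25 or −40. The full mean is (11 × −5 − 25)/12 = −6.7, or (11 × −5 − 40)/12 = −7.9. Without the twelfth patient it is −5.0.

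**The case against.** The strongest points on the other side:

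- **Recording is an inference.** No passage says an aborted stand becomes a blank. Staff might take an early or unscheduled reading. SAP 9.1 uses unscheduled readings for notable values, which partly protects the Table 3 flags. It does not say that they feed the separate orthostatic criteria, and it helps only if a reading was taken.
- **The event is captured elsewhere.** Protocol 3.7.3.7 makes clinically significant vital-sign changes AEs, SAP 7.9.1 tabulates them by cycle, and all assessments are listed. In 12 patients each gap can be traced. This stands, but it does not correct the BP-criterion counts. The number missing does not separate symptoms from other causes, and a patient with some standing readings may not appear as missing in a count over all timepoints.
- **The missing-at-random wording drives no model.** Correct: the analyses are descriptive. The understatement comes from counting available readings only, and the wording presents that as harmless.
- **An unmeasured stand is not a measured fall of more than 20 mm Hg.** Also correct, so it should not be folded into any of the three measured criteria.

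A reader might infer that the worst orthostatic reactions are, as a rule, scored as non-events. The documents do not support that. It is true only of patients with other, non-qualifying readings in the cycle, and in the illustration more than half of patients with an aborted stand are still flagged. Nor do the documents rank orthostatic hypotension as the main haemodynamic tolerability outcome, since the objectives carry no such hierarchy. A missing BP beside a dizziness AE leaves that AE uncorroborated but does not contradict it.

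**Conclusion.** The point holds in a limited form. For standing readings lost to symptoms, missing at random is not credible. The available-reading rule can then understate the orthostatic and standing low-BP counts and the mean orthostatic fall, and in one direction only. Unscheduled readings and AE tables mitigate this in part.

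The size is unknown, because neither document says how an aborted stand is recorded or how often one is expected. A wholly missed patient costs up to 8.3 points in a cycle of 12. The assumed models give a range from under 1 to about 14 points, mostly below 5. The upper end should not be read as an expected value: it needs a mean fall of 12 mm Hg and every fall beyond 25 mm Hg to be aborted. The case for a change rests on the known direction of the error, the weight of one patient, and the low cost of the remedy.

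**What to change.** In SAP 6.3 and 7.9.3:

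1. Classify each missing scheduled standing reading, using the explanation Protocol 5.3 already asks for, as due to symptoms or inability to stand, or as due to another reason. Readings missing for other reasons stay missing.
2. Report by cycle group a separate row: patients with a standing measurement not completed because of symptoms.
3. Keep the measured-only counts for the systolic, diastolic and pulse criteria, and state their denominator.
4. Add one composite count: any measured orthostatic BP criterion met, or standing not completed because of symptoms. The denominator is all patients dosed in that cycle.
5. Footnote the mean orthostatic summaries in SAP 7.7.2 with the number of symptom-related missing readings per cycle and timepoint.

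The cost is SAP wording, one derived flag, one table row and one extra count. Protocol 5.3 does not describe a coded reason field, so free-text explanations may need classifying under a rule written before the tables are run. The composite mixes measured falls with inability to stand, which showing both counts side by side resolves. The change concerns recording and counting only and leaves clinical management untouched.
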